8.3.21 Analysis of PGIC

The response category for each item of the PGIC will be summarized by treatment group and week.

Definition of PGIS 8.3.22

The PGIS will be completed at Baseline and on a weekly basis following the completion of all patient symptom diary items. Only subjects in selected countries who participate in the completion of the patient symptom diary will participate in the completion of the PGIS.

The PGIS is a five-item instrument that will ask the participants to think about their psoriasis related symptoms (including itching, pain, scaling, and sleep loss) over the past week and an additional five items asking about the same set of symptoms at the current point in time. Each item has five response categories ranging from "No (symptoms)," "Mild (symptoms)," "Moderate (symptoms)," "Severe (symptoms)," to "Very severe (symptoms)."

Analysis of PGIS 8.3.23

The shift from Baseline in response category to each relevant visit will be summarized by question, treatment group and week.

Confidential Page 38 of 63

PHARMACOKINETICS AND PHARMACODYNAMICS

All PK and antibody (AB) data will be listed together.

9.1 **Pharmacokinetics**

Bimekizumab plasma concentrations will be summarized for each treatment at each scheduled visit as described in Section 3.1 using the PK-PPS analysis set.

If bimekizumab plasma concentration measurements are deemed to be below the level of quantification (BLQ), then for calculation of the derived statistics this sample result will be set to half the LLOO. The subjects with at least 1 result that is defined as BLO will also be listed within the respective analysis table. Descriptive statistics will be calculated if at least 2/3 of the values are above the LLOO. If this is not the case, only median, minimum, and maximum will be presented.

In addition geometric mean bimekizumab plasma concentration time curves will be plotted by treatment group, and by cumulative antibody status for subjects randomized to bimekizumab.

The bimekizumab concentrations will also be listed.

Additional PK analyses will be described in the DAP.

9.2 **Pharmacodynamics**

IL-17A, IL-17F, IL-6, and IL-23 data will be summarized for each treatment at each scheduled visit using the PD-PPS analysis set.

Additional PD analyses will be described in the DAP

Immunogenicity 9.3

10.1.2 Number of doses received

The number of injections received will be summarized by treatment group over the 12 week administration period. There is anticipated to be 3 injections per dosing visit.

Exposure days at risk 10.1.3

For subjects who complete the Week 12 Visit and continue to the extension study, exposure days at risk will be calculated as:

Date of Week 12 Visit 1 Date of first administration of study medication+1 (13) ¹ and the extension study administration of study medication.

For subjects who discontinue on or prior to the Week 12 Visit for reasons other than death, exposure days at risk will be fixed as 84 days (which is equivalent to the intended 12-week initial period). This method is used to provide balance for the comparison of the exposure denominator for the initial period.

For subjects who die prior to the Week 12 Visit, exposure days at risk will be calculated as:

Date of death
$$-$$
 Date of first administration of study medication+1 (14)

Adverse events

Treatment-emergent adverse events

nis docum A-An AE is any untoward medical occurrence in a subject or clinical investigation subject administered a pharmaceutical product that does not necessarily have a causal relationship with this treatment. An AE can therefore be any unfavorable and unintended sign (including an abnormal laboratory finding), symptom, or disease temporally associated with the use of a

> Confidential Page 40 of 63

medicinal (investigational) product, whether or not related to the medicinal (investigational) product.

Treatment-emergent AEs (TEAEs) are defined as those AEs that have a start date on or following the first administration of study treatment through the final administration of study treatment + 140 days (covering the 20-week SFU period). If it is not possible (due to partial dates) to determine whether or not an AE is treatment-emergent then it will be assumed to be a TEAE.

To allow for a fair comparison across all subjects, exposure at risk for defining treatment-emergence will be cut off at the Week 12 Visit. Subjects who discontinue prior to the Week 12 Visit will also have their treatment-emergence cut off at Week 12 (84 days). All events that occur on the date of the Week 12 visit, with the exception of those with a HLT of injection-site reactions or any event that meets the criteria for anaphylactic reaction as defined in the AEs of Special Monitoring, will be considered treatment emergent and will be captured as part of the PS0011 study.

An overview of TEAEs that emerge following the 12-week treatment period (Post-Treatment Period) but within <140 days of the last dose (while sill in he PS0010 study) will be summarized separately. However, subjects who consent to the PS0011 extension study will have any Post-Treatment Period AEs reported only within the extension study to prevent duplicate reporting.

Adverse drug reactions (ADRs) are defined as a response to a drug which is noxious and unintended and which occurs at doses normally used in man for prophylaxis, diagnosis, or therapy of disease or for modification of physiological function. Any AE that is considered "Related" to study treatment will be classed as an ADR.

If the intensity of an AE is unknown, it is considered as severe.

If the relationship to study drug is missing, it is considered as related.

Subject time at risk represents the time a subject was at risk for having an AE. The definitions for subject time at risk (in days) are outlined in Section 10.1.3. These definitions will be used for exposure-adjusted AE summaries.

Selected AE summaries will include the exposure adjusted incidence rate (EAIR) with associated 95% confidence interval and the exposure adjusted event rate (EAER).

The EAIR is defined as the number of subjects (n) with a specific AE adjusted for the exposure and will be scaled to 100 patient-years:

$$EAIR = 100 \times n / \sum_{i=1}^{N} \left(T_{Exp(i)} \right)$$
 (15)

If a subject has multiple events, the time of exposure is calculated to the first occurrence of the AE being considered. If a subject has no events, the total time at risk is used.

Exact Poisson 95% confidence intervals for incidence rates are calculated using the relationship between the Poisson and the Chi-square distribution (Ulm, 1990; Fay and Feuer, 1997):

Confidential

$$UCL = \chi_{2(n+1),1-\alpha/2}^{2}/2$$
(17)

For each subject and each AE, the worst severity recorded will be attributed and used in the by-severity summaries. Similarly, the worst causality (most related to treatment) will be attributed and used in the by-causality summaries. If severity or causality is missing, the worst case will be assumed.

The following are AEs of special monitoring (AESM) that require special statistical analyses:

1. Serious infections, including TB and opportunistic infections

Serious infections will be identified based on MedDRA classification (SOC "Infections and infestations") using the "Any SAE" table. A separate table does not need to be produced to summarize these events.

Fungal infections will be summarized in a stand-alone table which presents EAIR and EAER. The table will include all TEAEs which code into the High Level Group Term (HLGT) of "Fungal infectious disorders".

Opportunistic infections (including tuberculosis) will be summarized in a stand-alone table which presents EAIR and EAER. The table will include all TEAEs identified using UCB-defined search criteria as described in Section 12.2.

These events will be presented in two stand-alone tables which include EAIR and EAER:

2. Malignancies, including lymphoma.

These events will be presented in two stand-alone tables which include EAIR and EAER:

- One table will be based on the criteria SMQ = "Malignant or unspecified tumours (SMQ)"
- One table will be based on the criteria SMQ="Malignant tumours (SMQ)".

Note that the events included in the "Malignant tumours" table will be a subset of the events included in the "Malignant or unspecified tumours" table. The SMQ search should included all TEAEs which code to a PT included in the Scope=Narrow group within each SMQ.

The output tables will include 2 different overall incidence rows:

• The first overall incidence row will summer or "Any maliana" The first overall incidence row will summarize "Any malignancies (including unspecified)" or "Any malignancies" (depending on the table) and this row will summarize the incidence of all AEs flagged for inclusion in the table, regardless of the High Level Term (HLT) it codes to.

13 June 2017

PS0010

The second overall incidence row will summarize "Any malignancy (including unspecified, excluding non-melanomic skin cancers)" or "Any malignancy (excluding non-melanomic skin cancers)" (depending on the table) and this row will summarize the incidence of AEs flagged for

Major cardiovascular events will be presented in a stand-alone table which includes EAIR and EAER. The table will include TEAEs that are identified using the following UCB-defined criteria:

• All serious TFAEs 11.

- All serious TEAEs which code to a PT included in the Scope=Broad and/or Scope=Narrow groups of the following SMQs:
 - Haemorrhagic central nervous system vascular conditions (SMQ)
 - Ischaemic central nervous system vascular conditions (SMQ)
- All serious TEAEs which code to a PT included in the HLT "Ischaemic coronary artery disorders" except events coding to PT "Chest Pain" or "Chest discomfort"
- All serious TEAEs which code to a PT of "Cardiac failure congestive".

4. Cytopenias

These events will be presented in a stand-alone table that is based on the SMQ = "Haematopoietic cytopenias". The SMQ search should include all serious TEAEs which code to a PT included in the Scope=Broad and/or Scope=Narrow groups within the SMQ.

5. Neuropsychiatric events (in particular depression and suicide)

These events will be presented in a stand-alone table including EAIR and EAER. The table will be based on the SMQ = "Depression and suicide/self-injury (SMQ)". The SMQ search will include all TEAEs which code to a PT included in the Scope=Broad and/or Scope=Narrow groups within the SMQ.

6. Inflammatory bowel disease

These events will be presented in a stand-alone table which includes EAIR and EAER. The table will include all TEAEs which code into the HLGT of "Colitis excl infective".

7. Anaphylactic reaction

Anaphylactic reactions will be summarized together in a stand-alone table.

The first row within the body of the table will be labeled "Any hypersensitivity/anaphylactic reaction" and will represent the overall incidence of subjects who reported at least one hypersensitivity reaction or at least one anaphylactic reaction.

The second row within the body of the table will be labeled "Any hypersensitivity reaction" and will represent the overall incidence of subjects who reported at least one hypersensitivity reaction.

The third row within the body of the table will be labeled "Any anaphylactic reaction" and will represent the overall incidence of subjects who reported at least one anaphylactic reaction.

Confidential Page 44 of 63

13 June 2017 PS0010

Following these three overall incidence rows, all TEAEs that have been identified as either a hypersensitivity reaction or an anaphylactic reaction will be summarized (together – not broken out by type) by SOC, HLT and PT.

All TEAEs that either emerged on the same day as when a study medication injection reaction was received, or that emerged one day after a study medication injection was received, which code to a PT which contains the term "hypersensitivity" will be considered to be a hypersensitivity reaction and included in the summary table as an in-

b) Anaphylactic reactions

An algorithmic approach will be used to identify TEAEs that are considered to be anaphylactic reactions. PTs are separated into the 4 distinct categories (A, B, C, D) prior to the algorithmic approach being applied.

All TEAEs that either emerged on the same day as when a study medication injection reaction was received, or that emerged one day after a study medication injection was received, and which fulfill any of the 3 criteria described in Section 12.3 will be included in the summary table.

8. Hepatic events and DILI

Although not officially considered to be AEs of special monitoring but hepatic events are nonetheless considered to be interesting enough to be summarized in stand-alone tables.

Hepatic events will be summarized in a stand-alone table that includes all TEAEs in the SMQ "Drug related hepatic disorders - comprehensive search (SMQ)". Note that the following two sub-SMOs are to be excluded: "Liver neoplasms, benign (incl cysts and polyps)" and "Liver neoplasms, malignant and unspecified (SMO)".

The SMQ search should include all TEAEs (regardless of whether they have been judged as related to study medication or not) which code to a PT included in the Scope=Narrow group within each SMO.

Hy's Law cases are to be reported separately in the liver function test summary table (with adjudication for "Potential drug-induced liver injury (PDILI)" cases).

By-subject listings of all AEs, all TEAEs during the treatment period, all TEAEs that occurred within 140 days of the last dose during the post treatment period and within the TEAE window and all non-TEAEs will be provided. A by-subject listing of all ADRs will also be provided. In addition listings will be produced for AESM.

Deaths, serious adverse events, and other significant adverse events

- Deaths, serious adverse

 Deaths, serious adverse

 Incidence of Serious TEAT

 and PT

 TEAT Incidence of Serious TEAEs per 100 subject years During Treatment Period by SOC, HLT,
 - Incidence of Serious TEAEs per 100 subject years During Post-Treatment Period by SOC, HLT and PT (subjects not entering the extension study only)

Confidential

Page 45 of 63

- Incidence of Serious TEAEs During Treatment Period by SOC, HLT, and PT
- Incidence of Serious TEAEs During Treatment Period by Relationship SOC, HLT, and PT
- Low Death During Treatment Period by SOC, HLT, and PT
 Local Company of TEAEs Leading to Death by Relationship by SOC, HLT, and PT
 Incidence of Serious Adverse Drug Reactions During Treatment Period by SOC, HLT, and PT
 Incidence of Serious Adverse Drug Reactions During Treatment Period by SOC, HLT, and PT
 Incidence of Serious Adverse Drug Reactions During Treatment Period by SOC, HLT, and PT
 Incidence of Serious Adverse Drug Reactions During Treatment Period by SOC, HLT, and PT
 Incidence of Serious Adverse Drug Reactions During Treatment Period by SOC, HLT, and PT
 Incidence of Serious Adverse Drug Reactions During Treatment Period by SOC, HLT, and PT
 Incidence of Serious Adverse Drug Reactions During Treatment Period by SOC, HLT, and PT
 Incidence of Serious Adverse Drug Reactions During Treatment Period by SOC, HLT, and PT
 Incidence of Serious Adverse Drug Reactions During Treatment Period by SOC, HLT, and PT
 Incidence of Serious Adverse Drug Reactions During Treatment Period by SOC, HLT, and PT
 Incidence of Serious Adverse Drug Reactions During Treatment Period by SOC, HLT, and PT
 Incidence of Serious Adverse Drug Reactions During Treatment Period by SOC, HLT, and PT
 Incidence of Serious Adverse Drug Reactions During Treatment Period by SOC, HLT, and PT
 Incidence of Serious Adverse Drug Reactions During Treatment Period by SOC, HLT, and PT
 Incidence of Serious Adverse Drug Reactions During Treatment Period by SOC, HLT, and PT
 Incidence of Serious Adverse Drug Reactions During Treatment Period by SOC, HLT, and PT
 Incidence of Serious Adverse Drug Reactions During Treatment Period by SOC, HLT, and PT
 Incidence of Serious Adverse Drug Reactions During Treatment Period by SOC, HLT, and PT
 Incidence of Serious Adverse Drug Reactions During Treatment Period by SOC, HLT, and PT
 Incidence of Serious Adverse Drug Reactions During Treatment Period by SOC, HLT, and PT
 Incidence of Serious Adverse Drug Reactions During Treatment Period by SOC, HLT, and PT
 Incidence of Serious Adverse Drug Reactions During Treatment Period

The following listings will be provided:

- A by-subject listing of all AEs leading to discontinuation of study treatment
- A by-subject listing of all death data

10.3 Clinical laboratory evaluations

se report a are also rec, are also rec, any mandained authorization.

This document cannot be used to support any mandained authorization. All laboratory data recorded in the electronic case report form (eCRF) will be summarized. If any additional analytes to those in Table 10–1 are also recorded then these will be listed only.

Table 10–1: Laboratory measurements				
Hematology	Chemistry	Urinalysis		
Basophils	Calcium	Albumin		
Eosinophils	Chloride	Bacteria		
Lymphocytes	C-reactive protein	Crystals		
Atypical lymphocytes	Magnesium	Glucose		
Monocytes	Potassium	pH .atil		
Neutrophils	Sodium	Red blood cell		
Hematocrit	Glucose	White blood cell		
Hemoglobin	Blood urea nitrogen	Urine dipstick for pregnancy		
		testing ¹		
Mean corpuscular hemoglobin	Creatinine	XO.		
Mean corpuscular hemoglobin concentration	Alkaline phosphatase	det		
	A amountate amin atman aforms a	2011		
Mean corpuscular volume	Aspartate aminotransferase (AST)	and		
Platelet count	Alanine aminotransferase	(0)		
	(ALT)			
Red blood cell count	Gamma glutamyltransferase			
	(GGT)			
White blood cell count	Total bilirubin			
	Lactate dehydrogenase			
	Total cholesterol			
	Serum pregnancy testing ¹			

¹ Pregnancy testing will consist of serum testing at the Screening and SFU visits. The pregnancy test will be urine at all other visits.

For tables where data are summarized by visit, unscheduled and repeat visits will not be summarized, but these data will be included in listings. For tables where multiple measurements over a period of time are considered (as in shift tables), unscheduled and repeat visits will be considered as long as they were collected in the period being summarized. All summaries will be presented in SI units and will be based on observed case values. In the case where laboratory values are below the lower limit of quantification, then these will be set to the midpoint between 0 and the lower limit of quantification for the purpose of summarizing the data. The following summaries will be provided:

- A summary of the absolute and change from Baseline values in each laboratory variable by treatment group and visit
- A summary of the number and percentage of subjects experiencing markedly abnormal values by laboratory variable, treatment group and visit
- A shift table of the number and percentage of subjects experiencing low, normal or high values at Baseline to maximum post-Baseline value (ie, low, normal, high), by laboratory variable and treatment group

13 June 2017 PS0010

- A Shift table of the number and percentage of subjects experiencing low, normal or high values at Baseline to minimum post-Baseline value (ie, low, normal, high), by laboratory variable and treatment group
- The End of Treatment value refers to the value from the last observed non-missing post baseline visit prior to the end of treatment.

 A by-subject listing of all laboratory data will be provided. The treatment group and will include:

laboratory variable, result (with abnormal values flagged as "L" or "H" accordingly) and unit.

A summary table highlighting the potential cases of Hy's Law, within each treatment group will be presented. Hy's Law is defined as.

- AST >3xULN or ALT >3xULN and
- Total Bilirubin >2xULN

Markedly abnormal values are defined as those with a severity of Grade 3 and above based on the common terminology criteria for adverse events (CTCAE) criteria (U.S. Department of Heath and Human Services 2010). Definitions of markedly abnormal values using the Grade 3 cutpoints are given in the tables below for age ranges of ≥17 years (Table 10–2 for markedly abnormal liver function tests values, Error! Reference source not found. for markedly abnormal hematology values and Table 10-4 for markedly abnormal biochemistry values). The laboratory results classified as Grade 3 or Grade 4 will be listed separately.

Table 10–2: Definitions of Marked Abnormal Liver Function Tests					
Parameter name	Conventional		Standard		
	Unit	Criteria	Unit	Criteria	Abnormal Designation
Alkaline Phosphatase		>5.0 x ULN		>5.0 x ULN	AH
ALT	U/L	>5.0 x ULN	U/L	>5.0 x ULN	AH
AST	U/L	>5.0 x ULN	U/L	>5.0 x ULN	AH
Total Bilirubin	mg/dL	>3.0 x ULN	umol/L	>3.0 x ULN	AH
GGT COL	U/L	>5.0 x ULN	U/L	>5.0 x ULN	AH

Table 10–3: Definitions of Marked Abnormal Clinical Chemistry Values					
Parameter name	Conventio	Conventional		Standard	
	Unit	Criteria	Unit	Criteria	Abnormal Designation
Creatinine	mg/dL	>3.0 x ULN	mmol/L	>3.0 x ULN	AH
Glucose	mg/dL	<30 >250	mmol/L	<1.7 >13.9	AL AH Jajiaji ^O
Calcium	mg/dL	>12.5 <7.0	mmol/L	>3.1 <1.75	AHÓ AL
Magnesium	mg/dL	>3.0 <0.9	mmol/L	>1.23 <0.4	AH AL
Potassium	mmol/L	>6.0 <3.0	mmol/L	>6.0	AH AL
Sodium	mmol/L	>155 <130	mmol/L	>155 <130	AH AL
Total Cholesterol	mg/dL	>400	mmol/L	>10.34	AH

Table 10–4: Definitions of Marked Abnormal Hematology Values					
Parameter name	Conventional		Standard		
	Unit C	Criteria	Unit	Criteria	Abnormal Designation
Hemoglobin	g/dL	<8.0	g/L	<80	AL
	Kany	>4.0 above ULN		>40 above ULN	АН
Lymphocytes Absolute	$10^{9}/L$	<0.5	$10^{9}/L$	<0.5	AL
50,		>20.0		>20.0	AH
Neutrophils Absolute	$10^{9}/L$	<1.0	$10^{9}/L$	<1.0	AL
Platelets	$10^{9}/L$	<50	$10^{9}/L$	<50	AL
WBC/Leukocytes	$10^{9}/L$	<2.0	$10^{9}/L$	<2.0	AL
anic		>100		>100	AH

Abbreviations: AH=abnormal high; AL=abnormal low; ALT= alanine aminotransferase; AST = aspartate aminotransferase; dL = deciliter; GGT: gamma-glutamyltransferase; L = liter; mg = milligram; mmol = millimoles; µg = microgram; ULN = upper limit of normal.

Confidential Page 49 of 63

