### 6.3.1 Potential drug-induced liver injury IMP discontinuation criteria

Subjects with potential drug-induced liver injury (PDILI) must be assessed to determine if IMP must be discontinued. In addition, all concomitant medications and herbal supplements that are not medically necessary should also be discontinued.

The PDILI criteria below require immediate and permanent discontinuation of IMP:

- Subjects with either of the following:
  - ALT or AST  $\geq 5xULN$
  - ALT or AST  $\geq 3xULN$  and coexisting total bilirubin  $\geq 2xULN$
- Subjects with ALT or AST  $\geq 3xULN$  who exhibit temporally associated symptoms of hepatitis or hypersensitivity. Hepatitis symptoms include fatigue, nausea, vomiting, right upper quadrant pain or tenderness. Hypersensitivity symptoms include fever (without clear alternative cause), rash, or eosinophilia (ie,  $>5\%$ ).

The PDILI criterion below allows for subjects to continue on IMP at the discretion of the Investigator.

- Subjects with ALT or AST  $\geq 3xULN$  (and  $\geq 2x$  baseline) and  $< 5xULN$ , total bilirubin  $< 2xULN$ , and no eosinophilia (ie,  $\leq 5\%$ ), with no fever, rash, or symptoms of hepatitis (eg, fatigue, nausea, vomiting, right upper quadrant pain or tenderness).

Evaluation of PDILI must be initiated as described in [Section 12.5.1](#). If subjects are unable to comply with the applicable monitoring schedule, IMP must be discontinued immediately.

Investigators should attempt to obtain information on subjects in the case of IMP discontinuation to complete the final evaluation. Subjects with PDILI should not be withdrawn from the study until investigation and monitoring are complete. All results of these evaluations and observations, as well as the reason(s) for IMP discontinuation and subject withdrawal (if applicable), must be recorded in the source documents. The CRF must document the primary reason for IMP discontinuation.

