### **12.1.2 Adverse events of special interest**

An AE of special interest (AESI) is any AE that a regulatory authority has mandated be reported on an expedited basis, regardless of the seriousness, expectedness, or relatedness of the AE to the administration of a UCB product/compound.

Potential Hy's Law, defined as  $\geq 3 \times \text{ULN}$  ALT or AST with coexisting  $\geq 2 \times \text{ULN}$  total bilirubin in the absence of  $\geq 2 \times \text{ULN}$  ALP, with no alternative explanation for the biochemical abnormality, must ALWAYS be reported to UCB as an AESI (ie, without waiting for any additional etiologic investigations to have been concluded). Follow-up information should then be reported if an alternative etiology is identified during investigation and monitoring of the subject.

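### The SAP's Hy's Law table uses a different case definition from the protocol's, so its count by arm may not match the reported AESIs

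*SAP*

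**What the plan says.** SAP 10.3 promises that "A summary table highlighting the potential cases of Hy's Law, within each treatment group will be presented". The definition that follows has two lines: "AST >3xULN or ALT >3xULN and" then "Total Bilirubin >2xULN". Both limits are strict. Nothing is said about ALP, about whether the two elevations must occur together, or about other causes.

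Protocol 12.1.2 also defines potential Hy's Law. It requires a value at or above 3xULN for "ALT or AST with coexisting" bilirubin at or above 2xULN. It adds that this is "total bilirubin in the absence of" ALP at or above 2xULN, and "with no alternative explanation for the biochemical abnormality". Such a case must be reported as an AESI without waiting for the work-up of cause to finish.

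Protocol 6.3.1 and Table 12-3 use the same inclusive 3x and 2x limits among their criteria for permanent discontinuation ("The PDILI criteria below require immediate and permanent discontinuation of IMP"), but without an ALP exclusion. A footnote to Table 12-3 asks only that ALP at or above 2xULN be discussed with the Medical Monitor as a possible sign of biliary obstruction.

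SAP 10.2.1 sends Hy's Law cases to the liver function test table and mentions adjudication of PDILI cases, without criteria. SAP 3.11, which lists departures from the protocol's analyses, does not mention Hy's Law. In the SAP amendment log, Change #18 replaced inclusive with strict limits only for Table 10-2 (markedly abnormal liver tests).

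**The concern.** Both documents describe potential cases of the same thing, yet the two rules select different subjects. Potential Hy's Law is the only AESI that the protocol names. The readable SAP text plans no separate AESI table, so the table in SAP 10.3 is the planned display of this event by arm. If its count differs from the number of AESI reports, a reader cannot tell whether the gap comes from the data or from the definition.

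The missing timing rule is a second problem. SAP 10.3 admits unscheduled and repeat visits to tables that consider several measurements over a period, and protocol Table 12-3 calls for liver tests at least twice a week once PDILI is suspected. A subject can therefore contribute many samples, and two programmers could pair them differently and reach different counts.

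**Working it through.** The plan states no figure to reproduce. The check is to write both definitions as rules and apply them to the same cases.

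**Rules**, in multiples of ULN (TB = total bilirubin):

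- Protocol 12.1.2: (ALT ≥ 3 or AST ≥ 3) and TB ≥ 2, coexisting, and not ALP ≥ 2, and no alternative explanation.
- SAP 10.3: (AST > 3 or ALT > 3) and TB > 2. The layout on two lines is taken to mean that bilirubin applies to either transaminase.

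**Cases**, with AST at 1xULN throughout. Unless stated, ALP is 1xULN, the elevations coexist and they are unexplained.

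| Case | Protocol 12.1.2 | SAP 10.3 |
|---|---|---|
| A: ALT 3.0, TB 2.5 | yes | no |
| B: ALT 4, TB 2.0 | yes | no |
| C: ALT 3.0, TB 2.0 | yes | no |
| D: ALT 4, TB 2.5, ALP 2.0 | no | yes |
| E: ALT 4, TB 2.5, ALP 3 | no | yes |
| F: ALT 4 and TB 2.5 at different visits | no | can be counted; no timing rule |
| G: ALT 4, TB 2.5, alternative explanation | no | yes, before any adjudication |
| H: ALT 4, TB 2.5 | yes | yes |

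**Omission (A to C).** A protocol case is lost only if TB is exactly 2xULN, or if the higher transaminase is exactly 3xULN. The documents give no ULN. If ALT is reported in whole units and the ULN is assumed to be 33, 40, 45 or 55 U/L, the critical value is 3 × ULN = 99, 120, 135 or 165 U/L. Such a result is attainable but should be uncommon.

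**Over-inclusion (D to G).** These cases do not depend on a boundary. D and E follow from the missing ALP condition, F from the silence on timing, and G from the missing condition on cause. G is the weakest: the protocol requires reporting before the cause is settled, so an explained case may already be among the AESI reports. Laboratory values alone cannot settle that condition.

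**Size.** With 40 subjects planned per arm, one subject is 1/40 = 2.5%. The documents give no expected rate. If an arm has no case or one case (an assumption), one misclassification moves it between 0% and 2.5%.

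**The case against.** The strongest reply is that SAP 10.3 describes a laboratory screen for review, and that a broad screen is the cautious choice. SAP 10.2.1 does mention adjudication, which could remove explained cases and perhaps cholestatic ones. This carries some weight against over-inclusion. However, no criteria are given, and review cannot recover a boundary case that was never flagged. The protocol's definition is also one of potential cases, yet it keeps the ALP and coexistence conditions.

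A second reply is that a missed case would not be hidden. This stands. The protocol requires PDILI events to be reported as AEs, and potential Hy's Law as an AESI and, where applicable, an SAE. The SAP also plans a hepatic events table, serious TEAE tables, a listing of AEs leading to treatment discontinuation and a full laboratory listing. A reader might infer that such a subject disappears from the report; the documents do not support that.

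A third reply concerns ALP. A reader might infer that subjects with ALP at or above 2xULN are not liver cases under the protocol at all. That goes too far: they can still meet the PDILI discontinuation criterion in protocol 6.3.1, which has no ALP exclusion. They fall outside the definition in 12.1.2 only. A row without the ALP condition is therefore legitimate, provided that it is labelled as such.

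A reader might also infer that high ALT at Week 2 with high bilirubin at Week 12 must be counted. The SAP does not say so. It is silent on timing, so such a pair can be counted.

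**Conclusion.** The point holds as an inconsistency between the two definitions that is neither declared nor explained. The SAP table can disagree with protocol 12.1.2 in both directions. Omission is confined to exact boundary values. Over-inclusion is the larger effect, through the ALP and timing conditions.

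The consequence is limited to a descriptive count, in which one subject is 2.5% of a 40-subject arm. A reader might infer that one misclassified subject changes the trial's conclusion. No test, threshold or decision rule depends on this table, so that does not follow. Nor does the table affect care: AESI reporting and discontinuation of study drug follow the protocol.

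The verdict assumes that the two criteria lines in SAP 10.3 are complete. Text shortly before them is garbled in the copy reviewed, but the lines themselves read as intact. No view is taken on which clinical threshold is right.

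**What to change.** Reconcile SAP 10.3 with protocol 12.1.2:

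- Use the same inclusive limits for the laboratory screen: at or above 3xULN for ALT or AST, and at or above 2xULN for total bilirubin.
- State what coexisting means for programming: same sample date, or a defined window.
- Show one row with the ALP condition and one without.
- Leave the absence of an alternative explanation to the adjudication mentioned in SAP 10.2.1, and state the criteria for that adjudication.

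If the strict and simpler rule is intended, list it in SAP 3.11 with its reason, and note under the table that its count need not equal the number of AESI reports.

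The cost is a change of wording and one extra table row. ALP is already in the chemistry panel (SAP Table 10-1), so no new data are needed.
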